Participants will receive 20 sessions of rTMS during the continued rTMS treatment phase (2 sessions daily, 5 days/week), and subsequently will undergo 24 sessions during the follow-up (FU) phase (two consecutive sessions per day for 12 weeks), for a total of 44 sessions over the course of the study.

The sham condition will match the number of pulses delivered during the 15Hz session and will use the same coil placement but the intensity of stimulation will be set a 3% of the individual resting motor threshold so to ensure that the participant will feel similar scalp sensations experienced by participants receiving active rTMS, but brain tissue will not be stimulated. rTMS will be used with the software necessary for the operator to remain blind to the stimulation condition. Also, the software will be pre-programmed by a staff member that will not be involved in data collection and analysis.

During each stimulation session and immediately after, hearth rate and blood pressure will be monitored. Also, at the end of the session, the 'Side Effect' questionnaire and the PANAS scale will be administered to evaluate potential side effects.

Side effects: The use of rTMS is considered safe when conducted within existing safety guidelines (Rossi et al. 2009). On the basis of these guidelines, it has been developed a screening tool, named the TMS safety screening, which will be administered to all study participants to determine their eligibility. Several side effects have been reported following TMS. The most important risk of rTMS is the possibility of inducing a seizure. The 1996 and 2008 International Consensus Safety Guidelines describe the maximum safe duration of an rTMS train based on intensity and frequency of the stimulation. Since the issuance of these guidelines, the incidence of TMS-induced seizures worldwide is very low, estimated as "rare" with low-frequency (< 1 Hz) rTMS and < 1% with high-frequency (> 1 Hz) rTMS. There have been no reports of any subject developing epilepsy or repeated spontaneous seizures after rTMS. All rTMS-induced seizures to date have been transient and self-limiting, without long-term sequelae.

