Concurrent medication has been implicated as a risk factor in some of the seizures reported with rTMS. Some have suggested that certain medications, e.g. tricyclic antidepressants and neuroleptics, should be contraindicated in those receiving rTMS. To minimize risk, psychotropic medications will be exclusionary criteria in the current study, and use of illicit drugs will be monitored. Although data are lacking, a history of epilepsy, of seizures of other

origin (other than febrile child fevers) could also be associated with an increase of TMS-induced seizures, and will therefore also be exclusionary criteria. To manage the small risk nevertheless present, a physician will be available while TMS sessions are in progress and will be called in the event of any medical issue.

Mild headache responding readily to non-opioid analgesics has been reported as onthe most common side-effect of rTMS reported in depression treatment trials. It may result from direct stimulation of superficial facial muscles or nerves, as rTMS may cause an uncomfortable facial twitch. Headaches usually go away promptly with nonprescription medication, such as acetaminophen, which will be offered to subjects as needed.

Hearing Impairment: Rapid excitation of the stimulation coil produces clicks that have resulted in transient increase in the auditory threshold of human subjects. This should not occur if earplugs are used. If a subject report or if an investigator observes that a subject's earplug has loosened or fallen out, investigators will immediately stop applying.

rTMS-Induced Manic Effects: Mania has been induced in a small number of healthy and depressed subjects by high-frequency rTMS to the left dorsolateral prefrontal cortex.

In all the above cases, the psychiatric side-effects induced by rTMS were transient, resolving with the cessation of rTMS or rapidly responding to pharmacological treatment.

Although not limited to, the risk for psychiatric complications appears to be existing predominantly in subjects with pre-existing psychiatric morbidity. An important means of minimizing risk in the current proposed study is therefore to exclude this population. Furthermore, mood symptoms will be monitored using a validated rating scale, and will provide an additional indication of hypomanic or manic symptoms (YMRS, PANAS, CPRS).

Research MR

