As time permits during the screening visit and after consenting, baseline characterization measures will also be collected. Participants may be scheduled for an additional visit and the necessary additional time to complete these assessments prior to beginning the 10-day rTMS treatment session. Following this, subjetes will have 8 follow-up visits [at the end of continued rTMS treatment phase, at rTMS follow-up visit #2, #4, #8, #12, and once a month during no rTMS follow-up phase].

Characterization measures include:

- Hamilton Anxiety Scale (HARS): A 21-item self-report inventory, which assesses the severity of anxiety. Completion time: ~ 5 minutes.
- Montgomery-Asberg Depression Rating Scale (MADRS): A clinical assessment to identify symptoms of depression. This assessment is especially useful in identifying changes in depression symptoms over time. Completion time: < 10 minutes.
- Positive and Negative Affect Scale (PANAS): A self-report scale to assess state-level affect. Completion time: < 5 Minutes.
- Profile of Mood States (POMS): A questionnaire designed to measure present mood state by a list of adjectives on a 5-point Likert scale and measures six dimensions of affect, including tension-anxiety, depression-dejection, anger-hostility, vigor-activity, fatigue-inertia, and confusion-bewilderment. The measure has been shown to produce reliable and valid profiles of mood state. Completion time: ~ 5 minutes.
- Snaith-Hamilton Pleasure Scale (SHAPS): A 14-item self-report scale designed to measure hedonic-tone/anhedonia. Completion time: ~ 5 minutes.
- Temporal Experience of pleasure Scale (TEPS): A 20-item self-report scale designed to evaluate individual trait dispositions in anticipatory and consummatory pleasure experiences. Completion time: ~ 15 minutes.

- Quality of Life Enjoyment and Satisfaction Questionnaire Short Form (Q-LES-Q-SF): A self-report scale designed to measure social ties between the participants and their friend, family, co-workers, etc. Completion time: ~ 15 minutes.
- Time-line follow back (TLFB). The TLFB will be used to assess substance use behavior. This assessment will be either self-administered or administered by one of the investigators. Participants will read the instructions and/or will be guided by the therapist or investigator in filling out the calendar. A lifetime TLFB will be administered at baseline and during each visit.
- Columbia-Suicide Severity Rating Scale (C-SSRS):to assess suicidality ideation.

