- Changes in CCQ score between the active rTMS and sham group, and from pre- to post treatment [baseline and after rTMS treatment: 2 weeks, 3 months, 6 months];
- Percent of negative urine samples between the active rTMS and sham group, and from pre- to post treatment [baseline and after rTMS treatment: 2 weeks, 3 months, 6 months].

Secondary aims:

- Changes in the scores on the 90 Symptoms Questionnaire (SCL-90) from pre- to post treatment [baseline and after rTMS treatment: 2 weeks, 3 months, 6 months];
- Changes in the scores of the Montgomery-Asberg Depression Scale (MADRS) from pre- to post treatment [baseline and after rTMS treatment: 2 weeks, 3 months, 6 months];
- Changes in the scores on the Hamilton Anxiety Rating Scale (HARS);

- Changes in the scores on the frontal assessment battery (FAB), and on the Flanker task from pre- to post treatment [baseline and after rTMS treatment: 2 weeks, 3 months, 6 months];
- Changes in the scores of the Iowa Gambling Task from pre- to post treatment [baseline and after rTMS treatment: 2 weeks, 3 months, 6 months];

Exploratory aims:

- DLPFC BOLD signal change in response to cocaine-related cues from baseline to each time point, and between the active and sham group;
- Changes in resting state functional connnectivity between the DLPFC and other nodes of the executive control network (ECN), from baseline to each time point, and between the active and sham group.

Statistical Analysis

Behavioral measures on each of the cognitive tasks as well as questionnaire data from each of the experimental conditions will be compared both within and between experimental groups using mixed, repeated-measures ANOVA, and linear mixed models. When assessing the statistical results from the behavioral and questionnaire data, a standard α -level of 0.05 will be used. Alpha-levels for multiple comparison follow-up tests will be corrected using an appropriate method (e.g., Bonferroni, Tukey, Scheffe).

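### Read literally, the plan analyses its side-effect and suicidality scales only as group means by ANOVA or mixed model at 0.05, and it plans no count by arm of participants harmed

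*Combined protocol and SAP*

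**What the plan says.** Under F. Objectives, Statistical Analysis, the data to be analysed are "Behavioral measures on each of the cognitive tasks as well as questionnaire data from each of the experimental conditions". They are to be "compared both within and between experimental groups using mixed, repeated-measures ANOVA, and linear mixed models", and "a standard α -level of 0.05 will be used", with correction for follow-up comparisons. The rest of the section covers imaging, correlations between clinical and neural measures, and power.

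Safety-related data are described elsewhere:

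- D. Procedures, rTMS: at the end of each session "the 'Side Effect' questionnaire and the PANAS scale will be administered to evaluate potential side effects". Also, "During each stimulation session and immediately after, hearth rate and blood pressure will be monitored".
- D. Procedures, Side effects: seizure is put at below 1% with high-frequency stimulation. Headache and hearing impairment are discussed. On mania, "Mania has been induced in a small number of healthy and depressed subjects by high-frequency rTMS"; mood is to be followed with the YMRS, PANAS and CPRS.
- D. Procedures, Questionnaires and Rating Scales: the characterization measures include "Columbia-Suicide Severity Rating Scale (C-SSRS):to assess suicidality ideation" and the BPRS.

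The Safety paragraph in G. Data Management and Safety measures deals with information, consent and ethics approval. No section plans a count of adverse events by arm, a per-participant incidence, a threshold on a safety scale, or a safety population.

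**The concern.** Seizure, mania and new suicidal ideation happen to individuals. What a reader needs to know is how many people in each arm had one, and how uncertain that number is. An arm mean spreads one person's large change over about 40 people, so a serious change in one or two participants hardly moves it. If the single analysis sentence is the whole plan for these instruments, the trial would hold session-by-session side-effect data for up to 44 sessions per participant without a summary suited to it. The plan itself notes that no sham-controlled study has assessed chronic rTMS in this population, so a randomized description of harms would be useful in its own right.

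**Working it through.** **1. The plan's own figure.** The power paragraph uses d = 0.65, alpha 0.05 and a one-tailed t-test, and arrives at about 30 per group. Power is not stated; assume 80%.

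n = 2(z₀.₉₅ + z₀.₈₀)² / d² = 2(1.645 + 0.842)² / 0.65² = 29.3, rounded up to 30. The noncentral t distribution gives power 0.800 at 30 per group. The figure reproduces, but it is an efficacy figure. The document gives no power or precision figure for harms.

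**2. What the mean comparison can see.** From the plan: 40 randomized per arm, about 30 per arm for analysis, alpha 0.05. Assumed: unit-SD normal scores, one time point, a two-sided test (the analysis sentence gives no sidedness), and k active participants shifted by s SD.

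- Shift in the arm mean = k × s / n. For k = 1, s = 3, n = 40: 3/40 = 0.075 SD.
- Observed difference needed for significance = t₀.₉₇₅,₇₈ × √(2/40) = 0.445 SD. At 30 per arm it is 0.517 SD.

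Share of 50,000 simulated trials with p < 0.05:

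| Shifted participants | Shift (SD) | Arm-mean shift, n = 40 | 40 per arm | 30 per arm |
|---|---|---|---|---|
| 0 | none | 0 | 5.0% | 5.0% |
| 1 | 3 | 0.075 | 5.0% | 5.1% |
| 1 | 5 | 0.125 | 4.8% | 4.6% |
| 2 | 3 | 0.150 | 6.9% | 7.5% |
| 2 | 5 | 0.250 | 8.4% | 8.7% |

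A larger shift in one person does not help, because an outlier inflates the SD as well as the mean.

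**3. What a count can say.** Exact (Clopper-Pearson) two-sided 95% limits:

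- 0/40: upper limit 1 − 0.025^(1/40) = 8.8%. For 0/30 it is 11.6%.
- 1/40: 0.06% to 13.2%.
- 2/40: 0.6% to 16.9%.

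**4. What a count cannot do.**

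- Against 0/40 on sham, 5/40 gives a two-sided Fisher p of 0.055; 6/40 gives 0.026.
- The chance of at least one case among 40 is 1 − (1 − p)^40: 33% at a true risk of 1%, 18% at 0.5% and 4% at 0.1%. Treating the plan's below-1% seizure figure as a risk per participant is an assumption, hence the range.

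**The case against.** The strongest reply is that the analysis sentence names no safety instrument. It follows a list of efficacy and cognitive aims, and safety is not among the objectives, so it may have been meant only for those outcomes. That reading is possible. On it, the safety scales have no stated analysis at all, and the same tables are needed. The Side Effect questionnaire is a questionnaire by name, and the PANAS, C-SSRS and BPRS stand under the Questionnaires and Rating Scales heading, so the literal reading is fair.

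Other replies stand in part:

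- The calculation is a t-test at one time point, not the planned repeated-measures model, so the rates are illustrative. The dilution by k/n still applies to any term that compares arm means.
- The plan also compares within groups. That too is a comparison of means.
- Headache is described as one of the most common side effects, so the calculation for one or two participants does not apply to it.
- The C-SSRS is listed as a characterization measure. Using it for safety is a reasonable reading, not the plan's label.
- No scale is tied to seizure, which needs event recording.
- Counts cannot test for a difference in rare harms at this sample size either. The gain is in description.

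A reader might go further and infer that the trial would miss its known harms, or would report a non-significant mean as evidence of safety. The document does not say so. It provides for a physician to be available during sessions and for mood monitoring, and it does not describe a safety report. Those measures manage patients and do not set out what is reported by arm, but predicted misreporting is not in the text.

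**Conclusion.** The point holds as a question of method. The only analysis that can be read as covering the side-effect and suicidality instruments is a test of means, which is poorly suited to harms in a few people, and no participant-level count by arm is planned. Under the stated assumptions, one badly affected active participant leaves the rejection rate at about 5%, and two raise it to about 7% to 8%. The result is similar at 30 per arm and for shifts of 3 or 5 SD.

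Two stronger readings are not supported. First, the 8.8% limit for 0/40 should not be set against a 1% seizure risk as a ratio: the plan gives only an upper bound for high-frequency rTMS and does not state it per participant. Second, the absence of a heart rate and blood pressure analysis is missing detail, not a wrong method; the plan says they are monitored, not that values are stored. This is a cheap improvement that should be made. It does not affect the efficacy analysis.

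**What to change.** In Statistical Analysis, exclude the safety instruments from the ANOVA/0.05 sentence and add a short safety paragraph. For all participants who received at least one session, report by arm the number and percent with:

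- each Side Effect item at least once;
- any recorded seizure or other adverse event;
- C-SSRS ideation not present at baseline;
- worsening from the pre-treatment baseline on the scales the plan ties to manic symptoms (YMRS, PANAS, CPRS), beyond a cut-off the sponsor fixes before unblinding.

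Use the pre-treatment baseline, not the first session, because the session questionnaires are completed after stimulation. The YMRS and CPRS appear in the side-effects text but not in the list of scales, so the sponsor should confirm that they are collected.

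Give exact 95% intervals for each arm and an interval for the risk difference. State that p > 0.05 is not read as absence of harm, and that 0/40 still has an upper limit of 8.8%. Summarise heart rate and blood pressure by arm if the values are recorded.

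Cost: SAP wording and one or two tables. Cut-offs must be set in advance and adverse events must be recorded, which the document does not now describe.

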 Completion time: < 5 min.
- Brief Psychiatric Rating Scale (BPRS- brief version): to assess psychiatric symptoms. Completion time: 15 min.
- Visual Analogical Scale for Food Craving (VAS food): to assess food craving.
 Completion time: ~ 5 min.
- Insomnia severity index (ISI): to evaluate sleep patterns and quality. Completion time:

 ∼ 3 min.
- Symptom Checklist-90-R (SCL-90-R): brief self-report psychometric instrument to evaluate a broad range of psychiatric symptoms and to measure the progress and outcome of psychiatric and psychological treatments. Completion time: ~ 15 min.

Executive and Cognitive Function will be assessed at baseline, at the end of continued rTMS treatment phase, at the end of rTMS follow-up phase and at the end of the no rTMS follow-up phase. Executive Function and Cognitive Assessment include:

- Frontal Assessment Battery (FAB): to assess frontal dysexecutive phenotype. Completion time: ~ 10 min.
- Eriksen Flanker Task (Flanker): to assess the ability to suppress responses that are inappropriate in a particular context. Completion time: ~ 15 min.
- Iowa Gambling Task: to assess decision-making process. Completion time: ~ 15 min.

E. Study Design

The study itself will consist of three phases.

- (1) an outpatient screening phase, during which patients will be screened to assess their eligibility to be enrolled in the study. This phase will include informed consent and randomization, and will conclude with baseline data collection.
- (2) a continued rTMS treatment phase, during which subjects will receive 20 stimulation sessions (2 daily, 5 days/week). In addition to this, participants will also attend self-help groups twice per week, as part of standard-of-treatment for CUDs.

During this phase, treatment response will be assessed by evaluating cocaine craving and consumption, psychiatric and medical symptoms and functioning.

(3) a follow-up phase of 24 weeks, which will be structured as following. During the first 12 weeks (rTMS follow-up) subjects will be asked to return to the Outpatient Clinic for an outpatient visit. During these visits, participants will undergo real or sham stimulation (two consecutive sessions per day), and will also attend self-help groups once per week.

During the following 12 weeks (no rTMS follow-up), participants will not receive TMS but behavioral and other data will be collected to observe long-term effects of rTMS.

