If subjects are unable or unwilling to attend these visits, they will be contacted by phone or email, and an attempt will be made to obtain measures in this manner.

F. Objectives

Primary: The primary goal of the current study is to investigate the effects of repetitive transcranial magnetic stimulation (rTMS) targeting the left DLPFC on cocaine craving. The co-primary goal is to investigate rTMS effect on cocaine consumption.

Secondary: Our secondary goals are to evaluate rTMS effects on: (1) mood; (2) cognitive functions.

Exploratory: Our exploratory goals are evaluating rTMS effects on: (1) BOLD response in DLPFC during tasks known to activate this area; (2) resting state functional connectivity between the DLPFC and nodes of the executive control networks.

Outcomes measures: Our primary outcomes will be: (1) change in craving score as measured by the CCQ from pre- to post treatment [baseline and after rTMS treatment: 2 weeks, 3 months, 6 months]; (2) changes in cocaine consumption as measured by TLFB self-reports and urine drug screen from pre- to post treatment [baseline and after rTMS treatment: 2 weeks, 3 months, 6 months]. Our secondary outcomes are: Changes in the scores on the 90

Symptoms Questionnaire (SCL-90) from pre- to post treatment [baseline and after rTMS treatment: 2 weeks, 3 months, 6 months]; (2) changes in the scores of the Montgomery-Asberg Depression Scale (MADRS) from pre- to post treatment [baseline and after rTMS treatment: 2 weeks, 3 months, 6 months]; (3) changes in the scores on the Hamilton Anxiety Rating Scale (HARS); (4) changes in the scores on the frontal assessment battery (FAB), and on the Flanker task from pre- to post treatment [baseline and after rTMS treatment: 2 weeks, 3 months, 6 months];

(5) changes in the scores of the Iowa Gambling Task from pre- to post treatment [baseline and after rTMS treatment: 2 weeks, 3 months, 6 months];

In addition, in order to investigate DLPFC engagement by TMS, the following exploratory outcomes will be analyzed: (1) DLPFC BOLD signal change in response to cocaine-related stimuli from baseline to each time point [baseline and after rTMS treatment: 2 weeks, 3 months]. (2) Change in resting state functional connectivity, from baseline to each time point (z-score) [baseline and after rTMS treatment: 2 weeks, 3 months].

1. Aims

Primary aim:

To determine the effects of rTMS on cocaine craving and consumption in patients with CUD.

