The imaging data will be pre-processed and analyzed with MatLab. All functional images will be directly registered upon high resolution MPRAGE anatomical scans obtained during the same imaging session. Location and intensity of activations from individual and/or grouped data will be translated into 3D stereotaxic coordinates. Functional images of activation-induced BOLD signal changes will be determined using cross correlation or multiple regression analyses. Differences in structural and functional measures between active rTMS and sham participants will be assessed using between group comparisons (e.g., independent samples t-tests). Correlation and multiple regression approaches will be used to test for an association between clinical assessment measures and task-specific neural

measures (e.g., correlation between cocaine craving scores and neural activation in the striatum).

Real vs Sham rTMS Power Analysis. Because no sham-controlled studies have been performed assessing the chronic effects of rTMS administration on behavioral or neurophysiological measures in patients with CUD, anticipating an effect size is difficult. However, open label studies have shown substantial behavioral changes in clinical populations and could have similar effects in reducing cocaine use. In order to capture a reliable effect while not committing a type II error, a medium-large effect size (Cohen's d = 0.65) will be used to calculate the necessary participants to compare real and sham iTBS treatments. Approximately 30 participants per group will be required to detect significant differences between these two independent groups at a nominal α level of 0.05 in a one-tailed t-test assuming a medium-large effect size. We anticipate approximately 80-85% retention rate at visit 24, based on previous studies conducted in similar patient populations by our group. Therefore, 80 participants will be recruited at baseline, 40 for real and 40 for sham iTBS, to acquire the necessary 30 participants in each group for analysis.

G. Data Management and Safety measures

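### CCQ craving, a primary outcome, is assigned both repeated-measures ANOVA and linear mixed models with neither primary and no baseline covariate; the cost is lost precision and an open choice of method

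*Combined protocol and SAP*

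**What the plan says.** One sentence of the Statistical Analysis section covers every cognitive and questionnaire measure: "Behavioral measures on each of the cognitive tasks as well as questionnaire data from each of the experimental conditions will be compared" within and between groups "using mixed, repeated-measures ANOVA, and linear mixed models". The CCQ is a 45-item questionnaire (Questionnaires and Rating Scales), so it falls under this sentence. No separate model is given for it.

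Under Aims, the primary CCQ comparison is "Changes in CCQ score between the active rTMS and sham group, and from pre- to post treatment", at baseline, 2 weeks, 3 months and 6 months. No covariate, fixed effects, covariance structure, analysis set or missing-data rule is stated, and none of the three post-baseline times is made primary. Alpha levels "for multiple comparison follow-up tests will be corrected using an appropriate method".

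For participants who do not attend follow-up visits, Study Design says "they will be contacted by phone or email, and an attempt will be made to obtain measures in this manner". The power analysis states: "We anticipate approximately 80-85% retention rate at visit 24". It sizes the trial at about 30 per group "in a one-tailed t-test assuming a medium-large effect size" with d = 0.65, and recruits 40 per arm.

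**The concern.** The two methods treat a missed visit differently. Standard repeated-measures ANOVA needs all four CCQ scores and deletes a participant who lacks any one; a mixed model keeps the scores that exist. Under the ANOVA, 2-week and 3-month scores already collected are discarded because a later visit is missing. Phone or email retrieval may shrink the problem, but no rule covers what stays missing.

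Baseline CCQ is collected in everyone by design, yet as written it is used only by subtraction or as one more time point. Adjusting for the same baseline usually gives a narrower interval from the same data.

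With two methods and no order between them, one arm difference can also have two p-values. The stated alpha correction concerns follow-up tests and does not settle which method is primary.

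**Working it through.** **Inputs from the plan.** d = 0.65; alpha 0.05, one-tailed; 30 per group required; 40 per arm recruited; 80-85% retention. **Assumed, because the plan does not give them:** that d applies to CCQ; the correlation r between baseline and follow-up CCQ; the ratio k of baseline SD to follow-up SD; the timing of loss.

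**1. The plan's own figure.** Power is that of a noncentral t with 2n - 2 degrees of freedom and noncentrality d x sqrt(n/2). At n = 30 this is 0.65 x sqrt(15) = 2.517, giving one-tailed power of 0.800. The stated 30 per group reproduces if 80% power was intended (the plan states no power).

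**2. What deletion leaves.** 80 x 0.15 = 12 and 80 x 0.20 = 16 participants lost, so 40 x 0.85 = 34 or 40 x 0.80 = 32 per arm. This equates loss at the last visit with an incomplete CCQ record; isolated missed visits would add to it and remote retrieval would reduce it.

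| n per arm | d x sqrt(n/2) | one-tailed power | two-sided power |
|---|---|---|---|
| 30 | 2.517 | 0.800 | 0.697 |
| 32 | 2.600 | 0.823 | 0.726 |
| 34 | 2.680 | 0.843 | 0.752 |
| 40 | 2.907 | 0.892 | 0.819 |

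The last row is the ceiling for a mixed model. It applies only at 2 weeks, and only if nobody is lost by then.

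**3. Later visits.** Assume 40, 36 and 32 per arm at 2 weeks, 3 months and 6 months. Generalised least squares on change with known covariance (compound symmetry and AR(1), r = 0.3 to 0.7) gives one-tailed power of about 0.87-0.88 at 3 months and 0.845-0.859 at 6 months, against 0.823 in the 32 completers. At 6 months the completers' standard error is 3-6% larger.

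**4. Bias.** Simulations with no true effect, 40 per arm and dropout depending on observed scores showed no material bias in the complete-case change. Its standard error was about 0-6% larger than that of a likelihood-type estimate. Other dropout patterns were not tested.

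**5. Baseline adjustment.** With follow-up SD 1 and baseline SD k, the variance of change is 1 + k^2 - 2rk and the adjusted variance is 1 - r^2. At k = 1 the ratio reduces to (1 + r)/2. Adjusted variance divided by change variance:

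| k | r = 0.3 | r = 0.5 | r = 0.7 |
|---|---|---|---|
| 0.7 | 0.91/1.07 = 0.85 | 0.75/0.79 = 0.95 | 0.51/0.51 = 1.00 |
| 1.0 | 0.91/1.40 = 0.65 | 0.75/1.00 = 0.75 | 0.51/0.60 = 0.85 |
| 1.3 | 0.91/1.91 = 0.48 | 0.75/1.39 = 0.54 | 0.51/0.87 = 0.59 |

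The reduction is 35% / 25% / 15% with equal SDs, and 0% to about 52% over the whole table. Chance baseline imbalance at 32 per arm inflates the adjusted variance by a simulated factor of 1.017, so the equal-SD ratios become 0.661, 0.763 and 0.864.

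**6. Two open methods.** Suppose the smaller of two p-values were reported at 2 weeks, with dropout unrelated to craving and both methods on change. The completer and all-data statistics correlate sqrt(32/40) = 0.894 or sqrt(34/40) = 0.922. The two-sided type I error is then 7.1% or 6.8%. With Bonferroni over three time points it is 5.5-6.1%, against 4.0-4.5% with one method.

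**The case against.** The strongest reply is that the plan has already paid for deletion. It recruits 40 per arm to keep 30, and 32 to 34 complete cases exceed 30. This stands: a reader might infer that the ANOVA leaves the trial short of its sample size, and the plan's figures show otherwise.

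A reader might also infer that deleting incomplete cases biases the arm comparison. Deletion does mean comparing a subset of those randomised, but the simulations in step 4 found no material bias. Bias remains possible under other dropout patterns; it is not demonstrated.

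Third, a reader might take 7% as the trial's type I error. Nothing in the plan says the smaller p-value would be chosen. The sentence joins the methods with a conjunction, so both may be reported. The inflation arises only if the choice follows the results, and the plan's correction of follow-up tests could reduce it.

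Fourth, the gain from baseline adjustment depends on r and on the SD ratio, neither of which the plan gives, and it can be nil. That stands as a limit on its size. The direction does not depend on them: apart from the small imbalance loss, adjustment is never less precise than change.

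None of this says which method decides CCQ.

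**Conclusion.** The point holds as one of efficiency and pre-specification. Two methods cover a primary outcome with neither primary, and no baseline covariate is named; this needs no assumption beyond the text. Deletion is a property of standard repeated-measures ANOVA rather than something the plan states, and it matters only if that method is used. One-tailed power is then 82-84%, against a ceiling of 89% at 2 weeks and about 85-86% at 6 months. Those figures assume that d = 0.65 applies to CCQ, and the 6-month figure also rests on the assumed 40/36/32 loss. Analysing change rather than adjusting for baseline costs more than this in most of the settings tabulated, but its size cannot be fixed from the documents. The planned sample size is not in error. The change should be made because it uses data already being collected and closes the choice before results are seen.

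**What to change.** For CCQ, name one primary linear mixed model on all randomised participants as allocated, using every available visit, with visit, arm-by-post-baseline-visit and adjustment for baseline CCQ. Two forms are acceptable:

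- Baseline CCQ as a covariate, with baseline-by-visit. A participant without a baseline score is dropped.
- Baseline CCQ as a response, with arm means constrained equal at baseline. Such a participant is kept.

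The equal-means constraint requires baseline CCQ to be taken before the first stimulation and to be unaffected by allocation. The SAP should say so, because Study Design describes the screening phase thus: "This phase will include informed consent and randomization, and will conclude with baseline data collection".

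Use an unstructured covariance with small-sample degrees of freedom (for example Kenward-Roger) and a stated fallback if it does not converge. At 32 per arm, a 3-df chi-square test of group by visit ran at about 6.5% error in a check, so large-sample tests should not be relied on. Name the one time point whose arm difference is the primary CCQ result. Repeated-measures ANOVA may stay as a supportive analysis.

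The cost is SAP wording and no new data. The model still assumes that dropout is explained by the observed data. How the urine co-primary is analysed is a separate issue.
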